15.3 Trial design and sample size calculations

The power and sample size calculation is based on the primary outcome measure of PFS. A median PFS time of 4.8 months is assumed on the control arm. This has been calculated from the raw data of the relevant population from a recent large UK study in SCLC (Lee *et al* 2009). The STOMP trial population will be those patients in the Lee study that were categorised as responders after 4 cycles of chemotherapy. This trial aims to detect an improvement in median PFS to 7.8 months for either of the two experimental arms. A one-tailed significance level of 10% was selected, however, to adjust for multiplicity in comparing the two experimental arms separately to the control arm, the calculation is based on a log-rank test with a one-tailed significance level of 5% (equivalent to a two-tailed level of 10%).

The PFS analyses will be performed when approximately 105 events per comparison have occurred. With 105 events per comparison (assuming 1:1 randomisation) there is 80% power to detect a difference in treatments at a 5% 1-sided significance level, if the true (alternate) hazard ratio was hypothesised to be 0.62 (a reduction in risk of progression of 38%). If the median PFS in the control arm is expected to be 4.8 months, this equates to a 3 month increase in median PFS. Assuming 105 PFS events occur, an observed hazard ratio of 0.72 (a 28% reduction in risk of progression) will give a 1-sided p-value <0.05 within the

STOMP Protocol

trial (a hazard ratio of 0.72 corresponds to 1.9 month increase in median PFS, assuming exponential distribution and proportional hazards).

With the duration of the trial set as 2.5 years (24 months accrual and 6 months follow up) it is estimated that the trial will require 75 patients per treatment arm. Therefore in total a target recruitment of 225 patients is estimated to be required for this trial.

The sample size has been calculated employing the methodology for exponential survival using median survival times reported in Machin D, Campbell MJ, Tan SB, Tan SH: Sample Size Tables for Clinical Studies, 3rd Edition, 2009.

STOMP Protocol

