15.4 Methods for analysis

All analyses will be carried out on an intention-to-treat basis. Median progression-free survival time and overall survival time will be reported using Kaplan-Meier estimates together with 90% confidence intervals. In addition the survival rates at 4 and 6 months will be estimated and provided with 90% confidence intervals. Progression-free survival will be compared for each treatment arm to the pooled control group using the log-rank test.

In addition to the log-rank test, analysis of PFS using a Cox proportional hazards model will be considered. This analysis of PFS will adjust for prognostic factors in addition to the trial stratification factors. These factors may include stage and performance status at diagnosis. Consideration will also be given to the use of an interval censored data approach to the analysis of PFS.

Once 105 PFS events have been observed then there will also be an interim assessment of overall survival. A further analysis of overall survival will be performed after a further 6 months of follow up.

Changes in performance status over time will be assessed using longitudinal methods of analysis and will account for informative dropout. AEs, as a whole, will be reported as the number of patients on each treatment arm experiencing each event at each grade. In particular, the difference in the number of patients experiencing at least one grade 3 or grade 4 AE will be estimated with a 95% confidence interval.

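### A prespecified Holm step-down would improve cheaply on the valid flat 5% test per schedule, raising the chance of showing both schedules from about 69% to 80%

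*Protocol*

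**What the plan says.** Section 15.3 sets the error rate in two parts. "A one-tailed significance level of 10% was selected, however, to adjust for multiplicity in comparing the two experimental arms separately to the control arm", and then "the calculation is based on a log-rank test with a one-tailed significance level of 5" per cent, which it equates to a two-sided 10%. It carries the 5% into interpretation by stating that, with 105 events, an observed hazard ratio of 0.72 reaches one-sided p below 0.05. The objective is disjunctive: "This trial aims to detect an improvement in median PFS to 7.8 months for either of the two experimental arms".

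Section 15.4 names the test: "Progression-free survival will be compared for each treatment arm to the pooled control group using the log-rank test". It gives no test level, and the protocol mentions no step-down, hierarchy or passing on of error between the two comparisons. It does not use the word Bonferroni, but 10% / 2 = 5% for each comparison is that split.

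**The concern.** Under a flat split, the second schedule must still pass 5% after the first has succeeded. At that point only one hypothesis is left, and the chosen 10% family level would allow it to be tested at the full 10%. An active second schedule can therefore be called unsuccessful when the selected error rate does not require it.

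Both schedules working is a realistic case. Section 1.4 reports that 300 mg bd and 200 mg tds tablets were considered similar in tumour shrinkage in an ongoing study. If one schedule passes and the other just misses because of the stricter threshold, readers may see a difference between schedules that the data do not show.

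**Working it through.** **Inputs.** From section 15.3: control median 4.8 months, target 7.8 months, 105 events per comparison, one-sided 5% per comparison within a selected 10%, and 75 patients per arm. From section 5.4: allocation 2:1:2:1, which is 1:1:1 once placebo is pooled. Assumption: correlation 0.5 between the two log-rank statistics. The protocol does not state it, but two equal arms sharing an equal control imply it. Values of 0.4 and 0.55 are shown as a range.

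**The protocol's own figure.** The unrounded hazard ratio is 4.8 / 7.8 = 0.6154. By Schoenfeld's formula with 1:1 allocation, events = 4 × (1.645 + 0.842)² / (ln 0.6154)² = 105, with power 80.0%. With the rounded 0.62, 105 events give 78.9%. The critical hazard ratio at 5% is exp(−1.645 × 2 / √105) = 0.725, against 0.72 stated. The calculation reproduces.

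**Both schedules at the design effect.** Each Z has mean (√105 / 2) × ln(7.8 / 4.8) = 2.487.
- Flat rule, both shown: P(Z1 > 1.645 and Z2 > 1.645) = 68.8%.
- Holm, both shown: the larger Z exceeds 1.645 and the smaller exceeds 1.282. This is 2 × P(Z1 > 1.645, Z2 > 1.282) − P(both > 1.645) = 2 × 0.7434 − 0.6875 = 79.9%.
- Power per schedule: 80.0% under the flat rule. Under Holm it is 0.8003 + (0.7434 − 0.6875) = 85.6%.
- At least one shown: 2 × 0.8003 − 0.6875 = 91.3% under either rule, because the first step is the same.

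**Sensitivity of the chance of showing both.**

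| Setting | Flat 5% | Holm |
|---|---|---|
| HR 0.615, correlation 0.4 | 67.7% | 79.4% |
| HR 0.615, correlation 0.5 | 68.8% | 79.9% |
| HR 0.615, correlation 0.55 | 69.3% | 80.2% |
| HR 0.62, correlation 0.5 | 67.3% | 78.7% |
| Simulated log-rank, 75 per arm, 24 + 6 months (about 123 events per comparison, correlation 0.49) | 75.2% | 84.7% |

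**Error rates, correlation 0.5.** With neither schedule active, the family error is 0.10 − P(both > 1.645) = 8.8% under both rules. With one active at the design effect, the flat rule wrongly declares the other with probability 5.0%. Holm does so with probability 0.05 + P(Z1 > 1.645, 1.282 < Z2 < 1.645) = 0.05 + (0.0974 − 0.0492) = 9.8%, within the selected 10%. Power for the active schedule is then 80.0% against 80.1%.

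**Second-step threshold.** The critical hazard ratio is exp(−1.282 × 2 / √105) = 0.78. For an estimate at that value, the upper 90% limit is exp(−0.250 + 1.645 × 0.195) = 1.07.

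**The case against.** The strongest reply is that nothing in the protocol is wrong. An equal split is a valid and familiar choice, 105 events is correct, and the stated aim of detecting improvement in either arm has the same 91.3% power under both rules. That all stands. Showing both schedules is not a stated objective, and the primary hypothesis in section 3.2 does not distinguish schedules.

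The gain also depends on both schedules working. If only one does, Holm adds almost nothing for it and nearly doubles the risk of a false claim for the other. That is a real cost. It lies within the 10% the protocol already accepts, but it must be disclosed.

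A flat 5% also fits the 0.72 threshold in section 15.3 and the 90% intervals planned in section 15.4, which Holm's second step would not. This stands too, and is a matter of wording and reporting.

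Finally, section 15.4 fixes no test level, and an analysis plan not shown here could add a step-down rule without disturbing the event calculation. The point is still fair, because section 15.3 itself states the split and carries 5% into interpretation.

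A reader might infer that the flat split wastes error because it spends only 8.8% of the 10%. That does not favour Holm, which also spends 8.8% when neither schedule works.

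**Conclusion.** This is a cheap improvement to a valid rule. At the same 10% family level, Holm rejects everything the flat split rejects and sometimes more. Its validity does not depend on the correlation between the comparisons. The gain is about 11 percentage points for showing both schedules and about 6 points of power per schedule. It rests on both schedules having the full design effect, 105 events per comparison and a correlation near 0.5.

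A reader might infer that the multiplicity adjustment is faulty or the trial underpowered for its aim. The protocol does not support that: the error rate is controlled, the event count reproduces, and power for the either-arm aim does not change.

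**What to change.** Add the Holm rule to section 15.3 or 15.4 before unblinding: test the smaller of the two one-sided p values at 5% and, only if it is significant, the other at 10%. Keep the sample size calculation at 5% per comparison.

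Two consequential edits are needed. Limit the statement about an observed hazard ratio of 0.72 to the first step, noting that the second-step threshold is about 0.78. Report the Holm-adjusted p value beside the hazard ratio and its 90% interval, since a second-step success can have an upper limit as high as about 1.07.

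The change needs no extra patients or events. Its statistical cost, stated openly, is the rise from 5.0% to 9.8% in the chance of wrongly declaring an ineffective schedule when the other works. It has to be prespecified; adopted after the results are seen, it would not be credible.

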15.4 Methods for analysis

All analyses will be carried out on an intention-to-treat basis. Median progression-free survival time and overall survival time will be reported using Kaplan-Meier estimates together with 90% confidence intervals. In addition the survival rates at 4 and 6 months will be estimated and provided with 90% confidence intervals. Progression-free survival will be compared for each treatment arm to the pooled control group using the log-rank test.

In addition to the log-rank test, analysis of PFS using a Cox proportional hazards model will be considered. This analysis of PFS will adjust for prognostic factors in addition to the trial stratification factors. These factors may include stage and performance status at diagnosis. Consideration will also be given to the use of an interval censored data approach to the analysis of PFS.

Once 105 PFS events have been observed then there will also be an interim assessment of overall survival. A further analysis of overall survival will be performed after a further 6 months of follow up.

Changes in performance status over time will be assessed using longitudinal methods of analysis and will account for informative dropout. AEs, as a whole, will be reported as the number of patients on each treatment arm experiencing each event at each grade. In particular, the difference in the number of patients experiencing at least one grade 3 or grade 4 AE will be estimated with a 95% confidence interval.

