5.4 Trial entry and randomisation procedure

Prior to recruitment of patients into the trial, the Principal Investigator for each site, or their designee, should have returned all required documentation to the STOMP Trial Office, and the site personnel involved with the STOMP trial must have received appropriate training.

Patient eligibility will be established before treatment randomisation and randomisation codes will be assigned strictly sequentially as patients become eligible for randomisation, with eligible patients being randomised in a 2:1:2:1 ratio according to the following pattern:

	300 mg BD	200 mg TDS	Total
Olaparib	33.3 % (2)	33.3 % (2)	66.6 %
Placebo	16.6 % (1)	16.6 % (1)	33.3 %

STOMP Protocol

Randomisation will be stratified by disease extent (M0 vs M1a/b with any T or N stage, please see Appendix 1 for the AJCC TNM staging for lung cancer) and prior radiotherapy (concurrent vs sequential vs none). The actual treatment given to individual patients will be determined by a randomisation scheme that has been loaded into the Cenduit Interactive Web Recognition System (IWRS) database which is, for the purposes of randomisation, accessed by Cancer Research UK Clinical Trials Unit (CRCTU) on behalf of randomising sites.

Randomisation Office: [name] (9 am till 5 pm Monday to Friday excluding University of Birmingham closed days)

A blockrandomisation will be generated and all sites will use the same list in order to minimise any imbalance in the number of patients assigned to each treatment group.

For all subsequent visits the web IWRS system should be used by the site research team to record visits and dispense the required medication.

The following information will be required at randomisation;

- Name of hospital, Investigator and person randomising the patient
- Confirmation that the patient is eligible for the trial
- Confirmation that the patient has given written informed consent
- An anonymised copy of the screening CT scan report (fax to [name] immediately prior to randomisation) to demonstrate response to prior treatment. The following should be clearly stated on the report: FAO: STOMP trial office, site name, patient's initials and date of birth.
- Confirmation of extent of disease and whether or not the patient has had any prior radiotherapy

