7.1.1 Screening (day -28 to 0, i.e. Randomisation Date)

The following assessments should be performed to assess eligibility during the screening period:

- Medical history including AE review (from time of consent) and concomitant medication review
- Physical examination (including height and weight) to assess fitness and ECOG performance status
- Blood pressure (supine), pulse and temperature
- The following tests should be conducted to confirm patient eligibility:
 - Hb
 - WBC
 - ANC
 - Platelet count
 - Calculated or measured creatinine clearance
 - AST/ALT
 - Total bilirubin
- Coagulation tests (APTT and INR) if clinically indicated (unless the patient is receiving warfarin)
- Peripheral blood smear to test for MDS and AML (if clinically indicated)
- Pregnancy test for female patients of child-bearing potential (see Section 6.4.1)

STOMP Protocol

- CT chest and upper abdomen (to include liver and adrenals) performed in accordance with RECIST 1.1 (see Appendix 3)
- Final confirmation of eligibility (at point of randomisation)

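### Section 15.4 commits only to a PFS log-rank test written without the randomisation strata, leaves the Cox model that would use them optional, and gives performance status at diagnosis as an example covariate although ECOG is collected at entry

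*Protocol*

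**What the plan says.** Protocol 5.4 sets two stratification factors: "Randomisation will be stratified by disease extent (M0 vs M1a/b with any T or N stage") and "prior radiotherapy (concurrent vs sequential vs none"). That is 2 × 3 = 6 strata. Section 4.1 names the same factors.

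Protocol 15.4 gives the PFS comparison as "Progression-free survival will be compared for each treatment arm to the pooled control group using the log-rank test". It says neither stratified nor unstratified. The next paragraph adds: "In addition to the log-rank test, analysis of PFS using a Cox proportional hazards model will be considered". Of that model it says "This analysis of PFS will adjust for prognostic factors in addition to the trial stratification factors", and of the prognostic factors, "These factors may include stage and performance status at diagnosis".

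Section 7.1.1 schedules a screening examination "to assess fitness and ECOG performance status". Section 7.1.2 and Table 7.1 schedule ECOG again before cycle 1. Neither Table 7.1 nor the forms list in Table 11.1 has an item for performance status at diagnosis, although a medical history is taken at screening.

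**The concern.** When allocation is balanced within strata that predict outcome, a log-rank test that ignores them tends to reject too rarely under the null and to lose power under the alternative. As 15.4 is laid out, the randomisation factors belong to an optional second analysis and the committed test stands without them. The design has little room for this: its power is 80% at the planned 105 events.

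The covariate wording raises a separate point. PFS runs from randomisation (15.1), which follows at least three cycles of chemotherapy and a complete or partial response (5.2.1). Performance status at diagnosis describes the patient before that treatment. ECOG at entry describes the patient at the start of the PFS clock and is already collected.

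At stake are some power in the primary comparison and the clarity of the adjusted estimate. The validity of the primary test is not in question.

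**Working it through.** **1. The plan's own figure.** Inputs from 15.3: medians of 4.8 and 7.8 months, one-sided 5%, 80% power, 1:1 within a comparison. The 2:1:2:1 allocation in 5.4 gives each olaparib arm 2 parts and pooled placebo 1 + 1 = 2 parts, so 1:1 is correct.

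- HR = 4.8/7.8 = 0.615.
- Schoenfeld: d = 4(1.645 + 0.842)²/(ln 0.615)² = 105 events, matching the protocol.
- With the rounded HR of 0.62, power at 105 events is 78.9%.
- Critical HR = exp(−2 × 1.645/√105) = 0.725, consistent with the stated 0.72.

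This is the ordinary formula without strata. Stratifying the test does not change the event target.

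**2. Assumptions.** The protocol gives neither stratum sizes nor prognostic effects. Assumed here: 60% M1; radiotherapy concurrent/sequential/none 50/30/20% in M0 and 5/45/50% in M1; 150 patients per comparison; uniform entry over 24 months; permuted blocks of four within the six strata; analysis at 105 events; treatment HR 0.62 within strata. There were 8,000 runs per cell, so the simulation standard error is about √(0.75 × 0.25/8000) = 0.5 points for power and √(0.05 × 0.95/8000) = 0.24 points for the level.

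**3. Results (unstratified / stratified by all six strata).**

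| M1:M0 HR | No RT : any RT HR | Power % | Gain from stratifying (points) | One-sided level % |
|---|---|---|---|---|
| 1.0 | 1.0 | 77.9 / 75.6 | −2.3 | 5.1 / 5.1 |
| 1.3 | 1.2 | 76.4 / 74.8 | −1.6 | 4.7 / 4.7 |
| 1.5 | 1.3 | 75.9 / 75.8 | 0.0 | 4.8 / 5.4 |
| 2.0 | 1.5 | 71.2 / 75.0 | +3.8 | 3.9 / 5.2 |
| 2.5 | 1.5 | 68.8 / 75.7 | +6.9 | 3.6 / 5.0 |

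**4. Other assumed effects.** With HR 0.615 within strata, 60% M1 and 12,000 runs per cell:

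| M1:M0 HR | No RT HR | Power % | Gain (points) | One-sided level % |
|---|---|---|---|---|
| 1.5 | 1.2 | 77.6 / 77.2 | −0.4 | 5.0 / 5.1 |
| 2.0 | 1.0 | 75.8 / 77.3 | +1.5 | 4.4 / 4.9 |
| 2.0 | 1.3 | 73.0 / 76.7 | +3.7 | 4.1 / 4.8 |
| 2.5 | 1.3 | 69.4 / 76.8 | +7.4 | 4.0 / 5.4 |

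A further set of runs at HR 0.615 with 60% M1 gave 79% v 77% with non-prognostic strata, 77% v 77% at M1 HR 1.5, 75% v 78% at 2.0 and 71% v 77% at 2.5. The unstratified level was about 4.3% in the last two.

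The stratified level of 5.4% in two cells is about two simulation standard errors above 5%. Six strata is a fine split here: under the assumed mix, M1 with concurrent radiotherapy would hold 150 × 0.60 × 0.05 = 4.5 patients. Hence the need for a merging rule.

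**5. The covariate.** No arithmetic applies. ECOG is scheduled twice around randomisation. Performance status at diagnosis is named as an example in 15.4 but has no item of its own in the schedule or forms list.

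**The case against.** The strongest objection is that 15.4 never says unstratified. Stratifying a log-rank test and merging sparse strata are details that a protocol may leave to the SAP, which was not available here. This stands against any claim that the protocol specifies an unstratified test. It does not remove the point, because 15.4 does say where the stratification factors go, and that is an optional model.

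The size can also be challenged. Section 15.3 sets the effect from overall medians, whereas the simulations place it within strata, which dilutes the overall HR to about 0.63 to 0.65. In 4,000 runs with the overall HR held near its planned value, power was 80% unstratified v 85% stratified at M1 HR 2.5 (overall HR about 0.61), and 83% v 85% at M1 HR 2.0 (overall about 0.60). The gain is then about 2 to 5 points above the design target. So much of the apparent fall from 80% to about 70% reflects how the effect is defined. A gain from stratifying remains under both definitions.

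Three further inferences are tempting but unsupported:

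- **That the adjusted hazard ratio would use an outdated covariate in place of the baseline one.** The covariate list is permissive and does not exclude entry ECOG. Performance status at diagnosis is a legitimate pre-randomisation covariate.
- **That stage merely repeats the extent stratum.** In Appendix 1, M0 covers every stage below IV, so stage separates patients within M0.
- **That the test gives up its nominal 5% level.** The simulated level is 3.6% to 5.1%, with no inflation.

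**Conclusion.** The point holds as a cheap improvement, not as an error. As written, the committed PFS test makes no use of the two randomisation factors, the analysis that would use them is optional, and entry ECOG is not named.

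The test is valid, at or slightly below the nominal one-sided 5%. With the treatment effect set within strata:

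- The loss of power is about 3 to 7 points (largest 7.4) at M1:M0 hazard ratios of 2.0 to 2.5. It is 1.5 points in the one scenario at 2.0 where radiotherapy has no effect.
- There is essentially no difference at about 1.5.
- A stratified test costs about 2 points if the strata are not prognostic.

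All of this rests on assumed stratum sizes and prognostic effects, since the protocol gives none. The case for stratifying is that the sponsor chose these factors for randomisation, and that the possible gain exceeds the possible loss.

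**What to change.** Amend 15.4, and align the SAP if it does not already say so:

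1. The primary PFS test is a log-rank stratified by disease extent and prior radiotherapy as recorded at randomisation. A rule for merging sparse strata (M1 with concurrent radiotherapy is the likely one) is set before unblinding.
2. Commit to a Cox hazard ratio using the same two factors, rather than leaving it for consideration.
3. In the adjusted model, name ECOG at trial entry as the performance-status covariate, defined as the last value on or before randomisation, because the pre-cycle 1 assessment can fall after it. Stage may stay as a candidate.
4. Keep the unstratified log-rank as a sensitivity analysis.

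The cost is a few sentences. No new data or patients are needed and the 105-event target is unchanged. The statistical price is the roughly 2-point loss of power if the strata prove non-prognostic.

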6.0 TREATMENT DETAILS

6.1 Treatment schedule

All STOMP treatments will be given in an outpatient setting and according to the schedule stated below. Treatment must start within the time limits defined in the eligibility criteria – no more than 42 days after day 1 of the last chemotherapy cycle, or 21 days after the last radiotherapy fraction (whether thoracic or cranial). For patients who receive chemotherapy followed by radiotherapy, the radiotherapy must begin within 35 days from the start of the last chemotherapy cycle. Where concurrent treatment is given, and radiotherapy and chemotherapy finish on the same day, the chemotherapy timeline should be followed.

Treatment with olaparib/placebo 300mg po bd or 200mg tds, continuously will be given until death, disease progression, unacceptable toxicities or withdrawal of patient consent up to a maximum of 2 years.

The tablets should be taken at the same times each day, with a glass of water. Tablets can be taken with a light snack but should not be taken with a heavy meal because of the potential effect of food on absorption. The tablets should be swallowed whole and not chewed, crushed, dissolved or divided.

If vomiting occurs shortly after the tablets are swallowed, the dose should only be replaced if all of the tablets can be seen intact and counted. Should any patient enrolled on the trial miss a scheduled dose for whatever reason (e.g., as a result of forgetting to take the tablets or vomiting), the patient will be allowed to take the scheduled dose up to a maximum of 2 hours after that scheduled dose time. If greater than 2 hours after the scheduled dose time, the missed dose is not to be taken and the patient should take their allotted dose at the next scheduled time.

Patients will continue with trial drug until objective disease progression occurs (determined by RECIST 1.1 – see Appendix 3), as long as in the Investigator's opinion they are benefiting from treatment and they do not meet any other discontinuation criteria.

Patients will remain blinded to the trial team until after the final analysis. No crossover to olaparib is permitted.

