10.2 Reporting Period

Details of all AEs (except those listed above) will be documented and reported from the date that the patient is consented into the trial until 28 days after the administration of the last dose of trial medication.

SAEs that are judged to be at least possibly related to trial treatment must still be reported in an expedited manner irrespective of how long after IMP administration the reaction occurred.

STOMP Protocol

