15.2 Definition of secondary outcome measures

Overall survival time is defined as the interval in whole days between the date of randomisation into the trial and date of death from any cause. Patients who do not die during the course of the trial will be censored at the date when they were last known to be alive. The median survival will be reported as will the six month survival rate, both of which will be calculated using the method of Kaplan-Meier estimation.

Performance status of the patient is classified by the clinician at each treatment visit according to ECOG definitions (Oken *et al.*, 1982). The trial will assess the change over time in this measure.

AEs will be recorded according to the definitions given in Appendix 4 of the protocol with grade of events recorded by CTCAE version 4.0. Treatments will specifically be compared in terms of the number of patients who experience at least one grade 3 or grade 4 AE.

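### The grade 3-4 AE comparison is a crude patient count over observation windows that lengthen with PFS, so if olaparib delays progression as planned, equal toxicity per month would show as an excess on olaparib.

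*Protocol*

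**What the plan says.** Section 15.2 of the protocol fixes the safety contrast: "Treatments will specifically be compared in terms of the number of patients who experience at least one grade 3 or grade 4 AE". Section 15.4 fixes the estimator: "the difference in the number of patients experiencing at least one grade 3 or grade 4 AE will be estimated", with a 95% confidence interval. Neither section sets a time window, an exposure denominator or a time-to-event method for AEs. Section 15.4 also tabulates every AE by grade and arm, but this is the only AE contrast that is given an estimate and an interval.

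Three other places determine how long a patient is observed for AEs:

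- Section 10.2: recording starts at consent and runs "until 28 days after the administration of the last dose of trial medication".
- Section 6.1: treatment "will be given until death, disease progression, unacceptable toxicities or withdrawal of patient consent up to a maximum of 2 years". Section 7.2 also ends trial treatment at progression.
- Section 15.3: "A median PFS time of 4.8 months is assumed on the control arm", and "This trial aims to detect an improvement in median PFS to 7.8 months for either of the two experimental arms".

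**The concern.** The AE window closes 28 days after dosing ends, and dosing ends mainly at progression. An arm that progresses later is therefore watched for longer and has more opportunity to record a first grade 3-4 event. The crude count mixes toxicity with time at risk, and the amount of mixing depends on the very effect that the trial is designed to show.

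This matters because section 3.2 makes safety and tolerability a stated secondary hypothesis. A reader of the final report would naturally take the difference and its interval as the toxicity cost of olaparib, when part of it could be extra observation time. Section 15.4 recognises a related problem for performance status, where the analysis is to allow for informative dropout, but makes no such allowance for AEs.

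**Working it through.** **Inputs.** From the protocol: medians of 4.8 and 7.8 months and 75 patients per arm (15.3), dosing cap of 24 months (6.1), and a 28-day tail, or 0.92 months (10.2). Assumed, because the protocol gives no figure: the placebo proportion with a grade 3-4 AE (20-50%) and a constant first-event hazard h, equal in both arms. Time to progression is taken as exponential, as in 15.3. The clock starts at first dose; the screening period after consent is common to both arms and is left out.

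**The plan's own figure.** With hazard ratio 4.8/7.8 = 0.615, one-sided 5% and 80% power, events = 4 × (1.645 + 0.842)² / (ln 0.615)² = 24.73 / 0.2357 ≈ 105. This matches section 15.3, so the medians are a sound basis for what follows.

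**Mean AE window.** With λ = ln 2 / median, the mean window is (1 − e^(−24λ))/λ + 0.92.

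- Placebo: λ = 0.1444, giving 6.71 + 0.92 = 7.6 months.
- Olaparib: λ = 0.0889, giving 9.92 + 0.92 = 10.8 months.
- Ratio: 1.42.

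**Probability of at least one event.** P = 1 − e^(−0.92h) × [λ/(λ+h) × (1 − e^(−24(λ+h))) + e^(−24(λ+h))]. For example, h = 0.05 per month gives 28.8% on placebo and 37.7% on olaparib. Solving h for each assumed placebo proportion gives:

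| Placebo | h per month | Olaparib, same h | Difference (points) | Ratio | 95% CI half-width, 75 per arm (points) |
|---|---|---|---|---|---|
| 20% | 0.032 | 26.9% | 6.9 | 1.34 | 13.5 |
| 30% | 0.053 | 39.0% | 9.0 | 1.30 | 15.1 |
| 40% | 0.080 | 50.3% | 10.3 | 1.26 | 15.8 |
| 50% | 0.116 | 60.6% | 10.6 | 1.21 | 15.8 |

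The half-width is 1.96 × √[(p₀q₀ + p₁q₁)/75]. The artefact is half to two-thirds of it. The interval would exclude zero against olaparib in about 17-25% of trials, against a nominal 2.5%.

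**How far this depends on the assumptions** (relative excess):

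- Declining AE hazard, placebo 20-50%: 24% down to 16% (Weibull shape 0.7), 17% down to 12% (shape 0.5).
- All AEs within the first 3 months: about 3%. Within the first 2 months: about 1%.
- Extra non-progression stopping on olaparib only, placebo 30-50%: 17% down to 12% at 2% per month, 7% down to 5% at 4% per month.
- PFS hazard ratio 0.72 (the smallest significant effect named in 15.3), placebo 20-50%: 23% down to 14%.
- AE analysis done at about 105 events, near month 25-26 with uniform 24-month accrual: window ratio about 1.28, and an excess of about 4 to 7 points (24% down to 16%) for h from 0.03 to 0.12.

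**The case against.** **The count is a legitimate quantity.** The number of patients who have a severe event over a treat-to-progression course describes real burden, and an unseen SAP may add exposure-adjusted summaries. This stands, and is why the count should be kept. It does not settle the matter, because the protocol itself names this count as the treatment comparison.

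**The size is not fixed.** A reader might infer that olaparib will show a 20-35% excess whatever happens. The documents do not support that. The figure is relative whereas the planned estimator is a difference, and it needs a constant hazard, a placebo proportion that the protocol does not state, and completed treatment. If toxicity is concentrated in the first weeks, the artefact almost vanishes.

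**The reverse bias.** A reader might also infer that early stopping on olaparib could hide harm. One can construct such a case: an AE hazard 1.5 times placebo (0.075 v 0.05), no PFS gain, and 10% per month stopping for toxicity gives 28.8% v 28.6%. But that rate has no basis in the protocol, and it treats stopping as unrelated to grade 3-4 events. Under section 6.2 the compulsory permanent stop follows unresolved or recurrent grade 3-4 events, and those patients are already counted. If stopping comes only after the event, the same scenario gives 28.8% v 38.4%. Stopping for lower-grade events is possible under section 7.4.2, but nothing in the protocol indicates that it would be large enough to mask an excess.

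**The obvious remedy can mislead too.** A first-event rate per patient-month assumes a constant hazard. If equal toxicity falls entirely in the first 3 months (hazard 0.2 per month), the planned PFS gain produces a rate ratio of about 0.75, a false advantage for olaparib, while the crude ratio is 1.03. This objection stands and shapes the fix.

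**Conclusion.** The point holds as a conditional one. The protocol fixes a crude patient count as its safety contrast over windows tied to PFS. If olaparib achieves the planned effect and has the same AE hazard as placebo, the count would show a spurious excess of about 7-11 percentage points (20-35% relative) once treatment is complete. That rests on a constant AE hazard, a placebo proportion of about 20-50%, and treatment ending essentially at progression in both arms. Earlier analysis, additional stopping on olaparib or early-onset AEs all shrink it, to about 1-3% relative when all events fall in the first 2-3 months. The protocol gives neither an AE rate nor an onset pattern, so the size cannot be known in advance; that is the reason not to let the crude difference stand alone. The primary PFS analysis is unaffected.

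**What to change.** In section 15.4, keep the number of patients with at least one grade 3-4 AE as description, and add for each olaparib arm against pooled placebo:

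1. Time from first dose to first grade 3-4 AE, with follow-up ending 28 days after the last dose, reported as a hazard ratio with 95% CI.
2. The proportion with such an event within a common early window, for example 12 weeks from first dose. With equal constant hazards of 0.03 to 0.12 per month and the planned PFS gain, this crude ratio is about 1.03, so nearly all of the artefact is removed.

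Do not base the comparison on a constant rate per patient-month.

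The cost is a few lines of text and one extra table, with no change to patients, visits or sample size. AE onset must be dated at least to the treatment cycle: section 7.1.3 describes one AE form per cycle and section 10.3.1.1 asks for the highest grade since the last visit, but the protocol mentions no onset date. Stopping for toxicity remains informative for the hazard ratio, and the early window serves as a check on that.
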